Based on results from the drug utilisation study (DUS)/survey study, the PRAC has requested marketing authorisation holders' (MAHs) to conduct a qualitative study to investigate adherence to PPP issues despite high awareness of the measures. The PRAC's request for a qualitative study stems from a recognition of the persistent issue of poor adherence to the PPP, despite high levels of awareness among healthcare professionals and WCBP as shown in the DUS/survey study. The committee seeks a deeper understanding of the underlying factors contributing to this low compliance to inform more effective interventions. By imposing a qualitative study, the PRAC aims to explore the nuanced barriers and drivers of adherence behaviour beyond mere awareness. This qualitative study allows for a comprehensive assessment of the socio-cultural, psychological, and systemic factors influencing adherence to PPPs.

This study, categorized as a Category 3 PASS, aims to utilize an implementation science framework, specifically aligning with the PRECEDE-PROCEED Model. By adopting the PRECEDE-PROCEED framework, the study seeks to support targeted interventions and improve PPP implementation in real-world clinical settings, addressing the persistent gaps in adherence to PPP measures while WCBP using oral retinoid therapies.

Research question and objectives:

Research question: In Europe, what are the barriers and reasons for low adherence to the oral retinoid therapy PPP measures from the perspectives of (i) healthcare professionals (HCPs) who prescribe or dispense oral retinoid therapy to women of childbearing potential (WCBP), (ii) WCBP who recently used or are currently using oral retinoid therapy, (iii) parents, guardians, or caregivers of adolescent WCBP who recently used or are currently using an oral retinoid therapy?

Objectives:

The overarching objectives for all three populations of this study are the following:

- P1. To describe the understanding of oral retinoid therapy PPP measures
- P2. To describe the perception of oral retinoid therapy PPP measures
- P3. To identify barriers and potential facilitators influencing adherence to oral retinoid therapy PPP measures

Study design:

This is a non-interventional qualitative cross-sectional study, using qualitative interviews conducted in multiple European countries (France, Germany, Poland, and Spain).

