9.1.1.1.2 Exclusion Criteria for HCPs Prescribing/Dispensing Oral Retinoid Therapy

HCPs will be excluded from this study if meeting the following criteria:

- Being an inactive and retired HCP / allied HCP at the time of the interviews;
- Having a conflict of interest with the study (i.e., being employed by regulatory bodies, and/or pharmaceutical companies).

9.1.1.2 *Inclusion/Exclusion Criteria for WCBP (aged 18-49) and Parents, Guardians, or Caregivers of Adolescent WCBP*

9.1.1.2.1 *Inclusion Criteria for WCBP (aged 18-49) and Parents, Guardians, or Caregivers of Adolescent WCBP*

As shown in Table 2 below, between 25-28 WCBP and 10 parents, guardians or caregivers of adolescent WCBP per country (France, Germany, Poland, and Spain) will be targeted, if meeting the following inclusion criteria described below:

For isotretinoin (n=15 per country, 60 WCBP across all countries):

- Being female sex aged 18 to 49;
- Currently or recently (within the last 6 months) using isotretinoin;
- Willing/consent to participate in this study.

For acitretin (n=5 per country, 20 WCBP across all countries):

- Being female sex aged 18 to 49;
- Currently or recently (within the last 6 months) using acitretin*;
- Willing/consent to participate in this study.

For alitretinoin (n=5-8 from France, Germany, and Spain, 0 from Poland, 20 WCBP across all countries):

- Being female sex aged 18 to 49;
- Currently or recently (within the last 6 months) using alitretinoin*;
- Willing/consent to participate in this study.

Parent, guardians, or legal caregivers of Adolescent WCBP (n=10 per country)

- Parent, guardian or legal caregiver of adolescent WCBP aged 13 to 17 who are currently or recently (within the last 6 months) using isotretinoin or acitretin;
- Willing/consent to participate in this study.

Table 2. Target WCBP Samples across oral retinoid medication and country

Target country	Target WCBP samples to be recruited*			
	Isotretinoin	Alitretinoin (Min/Max)	Acitretin	Total (Min/Max)
France	15	5 - 8	5	25-28*

Germany	15	5 - 8	5	25-28*
Poland**	15	N/A**	5	20
Spain	15	5 - 8	5	25-28*
Total	60	20	20	100

*Note that this is a target number which may change depend on success of recruitment at local level. Country-specific targets may vary to account for the alitretinoin variability per country, but the overall sample will be of 100 WCBP globally.

Table 2 does not include n=10 parents, guardians, or caregivers of adolescent WCBP from each country.

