**N/A: Not Applicable. Alitretinoin does not hold marketing authorisation in Poland. Thus, efforts will be made to recruit patients across France, Germany and Spain (between 5 and 8 per country), to ensure methodological robustness in interpreting results. A total of 20 WCBP taking or recently have taken alitretinoin will be recruited across all countries.

** Given the low prescription rates for these two retinoid treatments, the feasibility of identifying WCBP may be challenging. The following hierachal steps and sample boosting will be followed to achieve the sample population, and is described in detail in Appendix 2:*

1. Identify WCBP aged 18-49 using alitretinoin or acitretin (target 5 WCBP per country for acitretin and 5-8 WCBP in France, Germany, or Spain for alitretinoin);
2. If samples of WCBP per country cannot be enrolled, country-specific targets may be varied to account for an overall sample of 20 WCBP globally (representation per country included, while aiming to identify at least 5 WCBP using alitretinoin aged 35-49 globally);
3. Additional mitigation strategies that could be implemented includes targeting WCBP using alitretinoin or acitretin in the last 2 years or targeting an additional European country. This includes asking HCPs to provide information about this qualitative study to eligible WCBP for self-referral;
4. Identify WCBP aged 35-49 using isotretinoin with vignette descriptions of PPP measures for isotretinoin and/or acitretin;
5. Identify WCBP aged 18-49 using isotretinoin with vignette descriptions of PPP measures for isotretinoin and/or acitretin.

9.1.1.2.2 Exclusion Criteria WCBP (aged 18-49) and Parents, Guardians, or legal Caregivers of Adolescent WCBP

WCBP will be excluded from this study if they meet any of the following criteria:

Based on Template No.: RWI_TP_EPI0016
 Revision 1

Reference: RWI_WI_EPI0005

Effective Date: 15Jun2018

- WCBP does not have childbearing potential during the treatment course for oral retinoids (please see list of potential causes for losing childbearing potential in Appendix 1. List of potential causes for infertility in women);
- Unable to understand or comply to the study procedures, including the interview.

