9.1.2.2.2 Direct-to-Patient Recruitment (Patient Databases)

IQVIA's in-house Direct-to-Patient recruitment channel, *Global Perspectives*, will engage in identifying WCBP and parents, guardians, or caregivers of adolescent WCBP. IQVIA's *Global Perspectives* will reach out to potential participants through their extensive databases of patients and caregivers, as well as via social media, connections with local patient associations, and direct conversations with clinicians.

IQVIA's *Global Perspectives* will publicize the study through email newsletters, recruitment flyers, and/or social media posts (template for outreach available in Annex 5. Outreach template for adult WCBP, parents or guardians of adolescent WCBP and HCPs). The outreach materials will provide a link to an online study screener (Annex 6. Example of screeners which will be used). Eligible individuals will be directed to an online informed consent form (Annex 7. Examples of the informed consent forms used). Alternatively, verbal screening via telephone may occur before obtaining both verbal and electronic consent.

Proof of eligibility for study inclusion criteria will be required from participants. This might entail a physician's confirmation of treatment, a photo of the current prescription for oral retinoids, or a photo of their oral retinoid medication package. Upon qualifying and consenting to participate, IQVIA's *Global Perspectives* will record the participant's contact details - including name, address, email, and phone number - in a private patient portal respecting General Data Protection Regulation (GDPR) and will coordinate an interview with IQVIA's Patient Centered Endpoints Research team.

Recruitment across each demographic stratum will be closely monitored and the time required to recruit every five participants will be registered to understand whether recruitment is progressing according to the pre-defined study timelines. Recruitment will halt once the target number of participants is reached.

Should the initial recruitment strategies prove insufficient, a mitigation plan will be put into action to guarantee successful recruitment outcomes, as described in section 9.1.1.2.1.

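### The conflict-of-interest exclusion covers HCPs only, and health-care occupation is not a listed variable, so people who know the PPP from work can enter the patient and parent samples unmarked

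*Protocol*

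**What the plan says.** **HCPs.** Section 9.1.1.1.2 begins "HCPs will be excluded from this study if meeting the following criteria", and its second criterion is "Having a conflict of interest with the study (i.e., being employed by regulatory bodies, and/or pharmaceutical companies".

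**WCBP and parents.** Section 9.1.1.2.2 is headed for both groups, but its lead-in is "WCBP will be excluded from this study if they meet any of the following criteria". Two criteria follow: "WCBP does not have childbearing potential during the treatment course for oral retinoids" and "Unable to understand or comply to the study procedures, including the interview". The inclusion criteria in 9.1.1.2.1 cover sex and age, retinoid use and consent for women. For parents the criterion is "Parent, guardian or legal caregiver of adolescent WCBP aged 13 to 17 who are currently or recently" using isotretinoin or acitretin, plus consent. None mentions occupation, employer or conflict of interest.

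**Entry checks.** Section 9.1.2.2.2 states "Proof of eligibility for study inclusion criteria will be required from participants". Its examples all concern treatment: a physician's confirmation, a photo of the prescription or a photo of the package.

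**Variables.** Section 9.2.2.1 lists education and past participation in a PPP study among the participant characteristics, but not occupation or employer.

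**Objective concerned.** "P1. To describe the understanding of oral retinoid therapy PPP measures", which applies to all three populations.

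**The concern.** The protocol itself treats employment by a company or regulator as disqualifying for one population. It gives no reason why the same employment is acceptable in the other two. Annex 2 names 32 consortium companies, and nothing in the criteria stops an employee of one of them from being interviewed as a user or as a parent.

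Health professionals who use a retinoid, or whose daughter does, raise a related but separate question. They are not conflicted in the sense of the HCP rule, but they may know the PPP from their work. Their answers are then weak evidence of what the patient materials and consultations convey to someone without that background. If occupation is not recorded, a reader of the final report cannot tell how far reported understanding rests on such participants.

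The issue is the interpretation of P1, chiefly where results are broken down by country and molecule and the cells are small.

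**Working it through.** The protocol states no figure on this point, so there is none to reproduce. The check is a comparison of criteria followed by a sense of scale.

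**Step 1: criteria compared**

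| Item | HCPs | WCBP | Parents |
|---|---|---|---|
| Regulator or company employment excluded | Yes (9.1.1.1.2) | No (9.1.1.2.2) | No (9.1.1.2.2) |
| Named in the lead-in to their exclusion list | Yes | Yes | No, heading only |
| Occupation among listed variables (9.2.2.1) | Specialty, setting and years in practice | Not listed | Not listed |

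The recruitment sections (9.1.2.2 and Appendix 2) and the bias section (9.4.4) contain no occupational screen for women or parents.

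**Step 2: weight of one participant**, using the targets in 9.1.1.2.1 and Table 2

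- Acitretin in one country: 1/5 = 20%
- Parents in one country: 1/10 = 10%
- All WCBP: 1/100 = 1%

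**Step 3: chance that at least one is present.** Let p be the share of health-care workers among participants. The documents do not give p; 5-10% is an assumption, and participants are treated as independent. The chance of at least one in a cell of n is 1 − (1 − p)^n.

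- n = 5, p = 0.05: 1 − 0.95^5 = 1 − 0.774 = 0.226
- n = 5, p = 0.10: 1 − 0.90^5 = 1 − 0.590 = 0.410

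This p counts anyone working in health care. PPP-specific knowledge is rarer, and p says nothing about company or regulator employees, for whom the documents offer no basis for a figure.

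**Step 4: possible size of the overstatement.** Suppose a share f of a sample are insiders who all understand the PPP and the rest understand it at rate u. The apparent rate is f + (1 − f)u, so the overstatement is f(1 − u). Both inputs are assumed.

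- Whole sample, f = 2-10%, u = 50-90%: from 0.02 × 0.10 = 0.2 to 0.10 × 0.50 = 5 percentage points
- One insider in a cell of 5 (f = 0.20), same u: from 0.20 × 0.10 = 2 to 0.20 × 0.50 = 10 percentage points

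The study does not estimate a comprehension rate, so these figures show scale only.

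**The case against.** **The exclusions serve different purposes.** HCPs are interviewed in their professional role, where an employer's interest bears directly on what they report. A nurse who takes isotretinoin is a genuine user subject to the PPP, and removing her narrows the range of experience the sample should capture. This stands for health professionals and is why they should not be screened out. It is weaker for employees of the sponsoring companies, whose interest in the findings does not depend on the role in which they are interviewed.

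**The study is qualitative.** P1 is descriptive, sample size rests on code saturation, and one informed respondent does not delete codes that others raise. The interim rule on adding a country (9.2.3.2) uses shared top-five barriers, not comprehension in a cell of 5. This stands: no decision has been shown to change.

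**Knowledge is already high.** Section 7 reports 94.0% awareness against 77.8% adherence among surveyed women and caregivers. A well-informed woman who does not adhere helps explain that gap. This stands for P3, less so for P1.

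**A reader might infer that such participants cannot be identified in the analysis.** The documents do not support that. The list in 9.2.2.1 is open-ended, the database is built from the screeners (9.3), and the content of the Annex 6 screeners is not shown. They may ask about occupation. Even so, no protocol criterion would support excluding anyone on the answer.

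**The general risk is acknowledged.** Section 9.4.4 says volunteers may be more aware and allows a comparison with non-participants where possible. It does not mention occupation or conflict of interest among women and parents.

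**Conclusion.** The asymmetry is in the text and holds without any assumption: the criteria admit company and regulator employees to the patient and parent samples, and health-care occupation is not a listed variable. The consequence is modest. Overstated understanding is a plausible direction of bias that the documents do not quantify. It is probably small over 100 WCBP and most visible in cells of 5 to 10. The 23-41% depends on an assumed 5-10% share of health-care workers and gives only the chance that one is present.

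Two stronger conclusions are tempting and not supported. One is that the P1 findings will be materially inflated; nothing in the documents shows that. The other is that the existing conflict rule, once extended, deals with health professionals; it covers employment by regulators and companies only. This is a low-cost improvement, not a flaw that threatens the study.

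**What to change.** 1. In 9.1.1.2.2, extend the existing conflict-of-interest exclusion (employment by regulatory bodies or pharmaceutical companies) to WCBP and to parents, guardians and caregivers. Reword the lead-in to name both groups, so that it is clear which exclusions bind parents.
2. Add one screener item on health-care occupation, if Annex 6 does not already have it, and list the variable in 9.2.2.1.
3. Keep health professionals who are genuine users or parents of users. Describe P1 understanding with and without them, at least for each population as a whole, because removing one from a cell of 5 leaves only 4.

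The cost is one criterion line, one screener question, a few more screen failures and a small extra descriptive analysis. Keeping health professionals in the sample matters because acitretin and alitretinoin users are scarce enough for the protocol to plan sample boosting in Appendix 2.

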9.1.2 Recruitment and Study Enrolment

Recruitment will start after completing Heads of Medicines Agencies (HMA)-EMA catalogue registration following Ethics Committee approval.

9.1.2.1 Recruitment and Study Enrolment for HCPs

HCPs will be identified using IQVIA's proprietary HCP panel, OneKey. HCPs who have previously consented to be invited to participate in interviews and survey studies will be contacted by email or by telephone.

HCPs will be invited to participate in the study via an email newsletter, which will contain a link to confirm eligibility. If contacted by phone, the study background and objectives, the contact information for any questions, and the study procedures (eligibility criteria, study flyer, and interview content) will be summarized to HCPs. HCPs who agree will be sent an eligibility link by email. If the link confirming eligibility is not completed, the HCPs will be sent a reminder by email 3 times. An HCP will be considered unreachable if they have been contacted 3 times without response.

Once screened, eligible HCPs will be sent a link to an online informed consent and if they agree to participate, preferred interview times will be registered. A confirmation email with the date and time of the interview will be sent back to secure the interview.

The recruitment in each stratum (HCP specialty/country) will be closely monitored and the time required to recruit every five HCPs will be registered to understand whether recruitment is progressing according to the pre-defined study timelines. The recruitment in each stratum will be stopped when the target number is reached.

[figure not shown]
9.1.2.2 Recruitment and Study Enrolment for WCBP and Parents, Guardians, or legal Caregivers of Adolescent WCBP

WCBP and parents of adolescent WCBP will be identified via the following channels:

- IQVIA in-house Direct-to-Patient Recruitment channel
- Recruitment via HCP referral

Using its in-house recruitment service, IQVIA can locate potential participants through diverse avenues (primarily HCP and patient databases, along with social media and Patient Organizations), thus offering access to the study for prospective patients who are currently using Oral Retinoids from various sourcing channels, described in Figure 2.

Figure 2. Recruitment sources and strategy for WCBP (aged 18-49) and parents, guardians, or caregivers of adolescent WCBP

Additional recruitment and sample boosting stepwise approaches for the identification of WCBP (aged 18-49) using oral retinoids are described in Appendix 2. Stepwise identification and sample boosting approach.

9.1.2.2.1 Recruitment via HCPs Referral

Within IQVIA's network of preferred sites, HCPs will be approached by the recruitment team, who will provide them with recruitment flyers and/or email newsletters to disseminate to eligible participants. HCPs will examine the screener information and disseminate it to eligible WCBP or parents of WCBP. HCPs will encourage these potential participants to reach out directly to the recruitment team for further screening and consent procedures, as well as for any inquiries about the study. WCBP or parents of WCBP eligible to the study will receive a link to an online informed consent form, and upon agreement to participate, they will be able to select preferred interview times.

HCPs assisting in this process will receive remuneration in accordance with the fair market value for their time spent on recruitment activities.

9.1.2.2.2 Direct-to-Patient Recruitment (Patient Databases)

IQVIA's in-house Direct-to-Patient recruitment channel, *Global Perspectives*, will engage in identifying WCBP and parents, guardians, or caregivers of adolescent WCBP. IQVIA's *Global Perspectives* will reach out to potential participants through their extensive databases of patients and caregivers, as well as via social media, connections with local patient associations, and direct conversations with clinicians.

IQVIA's *Global Perspectives* will publicize the study through email newsletters, recruitment flyers, and/or social media posts (template for outreach available in Annex 5. Outreach template for adult WCBP, parents or guardians of adolescent WCBP and HCPs). The outreach materials will provide a link to an online study screener (Annex 6. Example of screeners which will be used). Eligible individuals will be directed to an online informed consent form (Annex 7. Examples of the informed consent forms used). Alternatively, verbal screening via telephone may occur before obtaining both verbal and electronic consent.

Proof of eligibility for study inclusion criteria will be required from participants. This might entail a physician's confirmation of treatment, a photo of the current prescription for oral retinoids, or a photo of their oral retinoid medication package. Upon qualifying and consenting to participate, IQVIA's *Global Perspectives* will record the participant's contact details - including name, address, email, and phone number - in a private patient portal respecting General Data Protection Regulation (GDPR) and will coordinate an interview with IQVIA's Patient Centered Endpoints Research team.

Recruitment across each demographic stratum will be closely monitored and the time required to recruit every five participants will be registered to understand whether recruitment is progressing according to the pre-defined study timelines. Recruitment will halt once the target number of participants is reached.

Should the initial recruitment strategies prove insufficient, a mitigation plan will be put into action to guarantee successful recruitment outcomes, as described in section 9.1.1.2.1.

9.2 Interview Procedure

Interviews will be scheduled based on a confirmed date and time once their eligibility and informed consent are confirmed. Participants with a scheduled interview will receive an online link prior to the interview including an online conference link and telephone number to join the interview on the date and time of the scheduled interview.

At the beginning of the interview, a trained moderator from the IQVIA team will:

- Verify consent verbally,
- Provide background information about the study,
- Provide the opportunity for participants to ask any questions concerning the study,
- Will obtain permission to audio-record the interview and subsequently to be transcribed, coded, analysed, and interpreted leading to a final written report of aggregated results,
- If applicable, will ask for permission if a second IQVIA team member may listen to the interview for training/quality assurance and/or notetaking purposes,
- Will inform the participants about the honorarium for their participation in the study.

One-on-one interviews will be conducted via web-enabled audio conference, which will be accessible via the internet and/or local telephone number, as preferred by the participating respondent. Semi-structured interview discussion guides will be used to support the interviews and content of the interview expected. Discussion guides will utilize a combination of open-ended questions to capture participants' responses in their own words and in-depth follow-up probing questions to encourage elaboration and clarification when necessary. The interview guides will not be pilot tested with external participants as this would preclude them from further participating in the study. See section 9.2.1 for a description of the IQVIA moderator qualification process and the use of mock interviews to facilitate familiarity with the discussion guide and the conduct of the interviews.

Interviews will be conducted in waves of approximately n=5 interviews per wave (and per country). This approach allows for iteration of the discussion guide questions and process as needed, especially after the first several interviews are completed or if local adaptations of the questions or probes are needed. As the remaining interviews are conducted, the interview team will regroup to discuss the interviews on an ongoing basis. In addition, the project team will review the interview data in between waves to determine whether any modifications to the interview questions are needed. When necessary, the interview questions will be modified to improve clarity and to be tested in the following wave(s) of interviews.

Once the interview is complete, the participants will be compensated for their time per fair market value, if allowed per country regulations.

